### 8.3 SAFETY AND OTHER ASSESSMENTS

Safety is evaluated at each visit by examination of the lower extremity to which test article is being applied, and through both spontaneous and elicited reporting of adverse events.

### 8.4 ADVERSE EVENTS AND SERIOUS ADVERSE EVENTS

#### 8.4.1 DEFINITION OF ADVERSE EVENTS (AE)

An Adverse Event is any untoward medical occurrence temporally associated with the use of an investigational medicinal product, whether or not considered causally related to that product. An AE can be any unfavorable and unintended sign (for example, an abnormal laboratory finding), symptom, or disease. The Investigator, or his/her designee, will document AEs. AE data will be entered onto the appropriate source and electronic case report form (eCRF). Adverse events will be coded using Medical Dictionary for Regulatory Activities (MedDRA).

All AEs should be followed during the trial period. The Investigator should use his/her discretion in ordering additional tests as necessary to monitor the resolution of such events. Event outcome at resolution or at time of last follow up will be recorded as event resolved, resolved with sequelae, ongoing at discontinuation, or death. Investigators should continue to follow up events of concern outside of the trial per their standard of care. The trial database may be finalized in these cases with events noted as ongoing.

The Investigator should consider adverse events both as they relate to the investigational product and as they relate to the procedures involved in the trial such as debriding tissue. The Investigator is responsible for determining initial relationship, expectedness, and severity of adverse events.

All adverse events must be reported regardless of whether or not they are considered to be related to the test article.

#### 8.4.2 DEFINITION OF SERIOUS ADVERSE EVENTS (SAE)

A serious adverse event (SAE) is defined by federal regulation as any AE occurring at any dose that results in any of the following outcomes: death, life-threatening AE, requires hospitalization or prolongation of existing hospitalization, a persistent or significant disability/incapacity, or a congenital anomaly/birth defect.

Important medical events that may not result in death, be life threatening, or require hospitalization may be considered an SAE when, based upon appropriate medical judgment, they may jeopardize the subject and may require medical or surgical intervention to prevent one of the outcomes listed in this definition. Examples of such medical events include allergic bronchospasm requiring intensive treatment in an emergency room or at home, blood dyscrasias or convulsions that do not result in subject hospitalization, or the development of drug dependency or drug abuse.

#### 8.4.3 CLASSIFICATION OF AN ADVERSE EVENT

##### 8.4.3.1 SEVERITY OF EVENT

The severity of all AE, will be assessed by the Investigator and should be classified as mild, moderate, or severe. Severity will be graded according to the following definitions:

- **Mild:** The subject experiences awareness of symptoms but these are easily tolerated or managed without specific treatment.
- **Moderate:** The subject experiences discomfort enough to cause interference with usual activity, and/or the condition requires specific treatment.
- **Severe:** The subject is incapacitated with inability to work or do usual activity, and/or the event requires significant treatment measures.

#### 8.4.3.2 RELATIONSHIP TO STUDY INTERVENTION

The relationship of the event to the investigational product should be determined by the Principal Investigator according to the following criteria:

**Not Related:** The event is most likely produced by other factors such as the subject's clinical condition, intercurrent illness, or concomitant drugs, and does not follow a known response pattern to the trial product which makes a causal relationship unlikely.

**Related:** The event follows a temporal relationship or known response pattern to the trial product, and cannot be reasonably explained by other factors such as the subject's clinical condition, intercurrent illness, or concomitant drugs.

#### 8.4.3.3 EXPECTEDNESS

As with the use of any human tissue, the possibility of infectious agent transmission cannot be completely eliminated although all screening and microbial testing results were satisfactory for the tissue and tissue donor. Possible significant adverse events include microbial infection and transmission of viral disease.

Expected adverse events non-related to the product are those post-surgical conditions consistent with any dermal debridement and excoriation of an ulcer. Potential adverse events for all research subjects in this trial intrinsic to the nature of DFUs: bleeding, hematoma, cellulitis, pain, deteriorating ulcer exudation, erythema, edema, infections including deep tissue infections (osteomyelitis), and occurrence of new ulcers.

#### 8.4.4 TIME PERIOD AND FREQUENCY FOR EVENT ASSESSMENT AND FOLLOW-UP

The occurrence of an adverse event (AE) or serious adverse event (SAE) may come to the attention of study personnel during study visits and interviews of a study participant presenting for medical care, or upon review by a study monitor.

All AEs including local and systemic reactions not meeting the criteria for SAEs will be captured on the appropriate case report form (CRF). Information to be collected includes event description, date of onset, clinician's assessment of severity, relationship to study product (assessed only by those with the training and authority to make a diagnosis) confirmed by the Principal Investigator,

and date of resolution/stabilization of the event. All AEs occurring while on study must be documented appropriately regardless of relationship.

Any medical condition that is present at the time that the participant is screened will be considered as baseline medical history and not reported as an AE. However, if the study participant's condition deteriorates at any time during the study, it will be recorded as an AE.

Changes in the severity of an AE will be documented to allow an assessment of the duration of the event at each level of severity to be performed. AEs characterized as intermittent require documentation of onset and duration of each episode.

The Investigator will record all reportable events with start dates occurring any time after informed consent is obtained until the final study visit. At each study visit, the investigator will inquire about the occurrence of AE/SAEs since the last visit. Event outcome at resolution or at time of last follow up will be recorded as "event resolved", "resolved with sequelae", "ongoing at discontinuation", or "death".

---

#### 8.4.5 ADVERSE EVENT REPORTING

Disease Related Events expected in this population (angina, neuropathy, nephropathy, urinary tract infection, erectile dysfunction, retinopathy, hypoglycemic events) may be reported by the investigator if they differ in nature or frequency from what is expected, or if they appear to have a causal relationship to the test article. All adverse events must be reported in the subject's source documents, and recorded on an Adverse Event Case Report Form regardless of whether or not they are considered to be related to the test article.

---

#### 8.4.6 SERIOUS ADVERSE EVENT REPORTING

In the event of any SAE reported or observed during the trial, whether or not attributable to the trial product, the Investigator, or designee, shall report the event to the medical monitor within 24 hours being made aware of the event. An initial report should be made with the understanding that it may be lacking in details.

A Serious Adverse Event Form must be completed for all serious adverse events and submitted within 24 hours of the Investigator's knowledge of the event and to the Institutional Review Board/Independent Ethics Committee, according to their reporting requirements. When new significant information is obtained as well as when the outcome of an event is known, the Investigator must provide this information as soon as it becomes available. Depending on the nature of the adverse event, copies of the subject's medical records as well as results of any relevant laboratory tests performed maybe required to be submitted. If the subject was hospitalized, a copy of the discharge summary should be forwarded as soon as it becomes available. In certain cases, a letter from the Investigator that summarizes the events related to the case may be required.

Serious adverse events must be reported using the eCRF system (preferred), or via telephone or email, to the following representative within 24 hours of the Investigator's knowledge of the event:

SAE reports shall be entered into the eCRF and hospital records will be submitted to:

The study Sponsor will be responsible for notifying the Food and Drug Administration (FDA) of any unexpected fatal or life-threatening suspected adverse reaction as soon as possible, but in no case later than 7 calendar days after the Sponsor's initial receipt of the information. In addition, the Sponsor must notify FDA and all participating investigators in an Investigational New Drug (IND) safety report of potential serious risks, from clinical trials or any other source, as soon as possible, but in no case later than 15 calendar days after the Sponsor determines that the information qualifies for reporting.

#### 8.4.7 REPORTING EVENTS TO PARTICIPANTS

All important changes to the risks associated with TTAX01 will be conveyed to study subjects through updated consent forms. Final results of the study will be provided to each investigator, who will then share individual results with study subjects.

#### 8.4.8 EVENTS OF SPECIAL INTEREST

Not applicable.

#### 8.4.9 REPORTING OF PREGNANCY

Pregnancy occurring during the study is not an adverse event, but it should be brought to the attention of the sponsor as soon as possible. The continuation of a subject who becomes pregnant will be determined on a case by case basis.

### 8.5 UNANTICIPATED PROBLEMS

#### 8.5.1 DEFINITION OF UNANTICIPATED PROBLEMS (UP)

The fundamental goal of this pilot protocol is to identify unanticipated problems with the protocol itself (e.g., clarity, contradictions) and with study procedures. Monitoring of the study will focus on the identification of such problems. Unanticipated Problems which place participants or others at a greater risk of harm (including physical, psychological, economic, or social harm) than was previously known or recognized may result in placing the study on hold, or study termination.

#### 8.5.2 UNANTICIPATED PROBLEM REPORTING

Investigators should report all unanticipated problems to the sponsor as soon as they are identified.

#### 8.5.3 REPORTING UNANTICIPATED PROBLEMS TO PARTICIPANTS

Not applicable.

## 9 STATISTICAL CONSIDERATIONS

### 9.1 STATISTICAL HYPOTHESES

This pilot study will utilize descriptive statistics in the analysis and reporting of observed outcomes, to be described in greater detail in a separate Statistical Analysis Plan.

### 9.2 SAMPLE SIZE DETERMINATION

It is expected that 47 potential subjects will be screened in order to find 36 who qualify for this trial (screen failure rate 30%). The target number 36 is selected based on the law of large numbers, which holds that sample sizes less than 25 are more likely to produce skewed distributions of observed values, while sample sizes greater than 25 should generate a bell shaped distribution of observed values whose mean approaches the expected value as sample size increases.

The dropout rate is expected to be ~10%. As numbers between 25 and 30 should yield reasonably equivalent estimates of efficacy, there is no plan to replace dropouts.

### 9.3 POPULATIONS FOR ANALYSES

The Intent-to-Treat (ITT) population will consist of all enrolled subjects. The ITT population is the primary efficacy population and will be used to conduct all analyses on primary and secondary efficacy endpoints.

The Per Protocol (PP) population is a subset of subjects in the ITT and is the secondary efficacy population. The PP population will be defined as all qualified and treated subjects meeting inclusion and exclusion criteria and completing the study treatment as planned in the protocol, with no major protocol deviations during the 16-week Treatment Period. Major protocol deviations will be determined by the trial clinical team prior to database lock. Subjects found to have major protocol deviations will be excluded from the PP population.

The Safety Population includes all subjects who underwent treatment, regardless of protocol compliance. The Safety Population will be used for the analysis of safety endpoints.

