### 7.2 PARTICIPANT DISCONTINUATION/WITHDRAWAL FROM THE STUDY

All subjects have the right to discontinue the trial at any time. The Investigator may also withdraw a subject from the trial at any time if they deem it medically necessary. The reason for discontinuation should be documented and trial staff should attempt to bring the subject in for an Early Termination Visit and perform all applicable assessments as appropriate listed under the End of Treatment Period Visit (Visit 19) for discontinuations that occur during the Treatment Period.

Subjects may be discontinued from the trial for the following reasons:

- Adverse Event (including illness)

- Subject withdrawal of consent
- The Sponsor or Investigator terminates the trial
- Lost to follow-up
- Product-related > Grade 2 skin or systemic allergic reaction
- Ulcer-related complications (i.e., life-threatening, infection-related sepsis complications)
- Subsequent limb amputation (i.e., full amputation involving the index ulcer anatomic location)

In the event of a subject's withdrawal, the Investigator will promptly notify the medical monitor and will make every effort to complete all procedures at either the End of Treatment Period Visit. Even if removed subjects have been removed from the trial or if an adverse event remains ongoing, Investigators should follow up with subjects as per their standard medical practice.

Discontinued subjects will not be replaced. Simultaneous screening at multiple sites may result in an allowable modest over-enrollment.

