3 STUDY POPULATION

3.1 Definition of Subject Populations

All subjects who have procedures completed at Visit BS are considered study participants. The following subject populations are defined to assess the safety and efficacy of TTAX01 with SC.

Safety Population

The safety population is defined as all subjects who are enrolled and who have received at least one treatment of the investigational product.

Intention-to-treat (ITT) Population

This population is defined as all subjects who are enrolled to receive treatment. The ITT population is the primary population for efficacy evaluation in this study. The ITT population will be identified and finalized before the database is locked.

Per-Protocol (PP) Population

This population is defined as sub-population of the ITT population. The PP population is the secondary population for efficacy evaluation in this study. The detailed criteria of the PP population will be provided in a separate "Data Standards" document completed prior to data base lock.

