4.5 Efficacy Results and Tabulations

4.5.1 Results of primary efficacy analysis

Descriptive and inferential statistics on the ITT population of the proportion of subjects with complete ulcer closure over the treatment period will be presented in Table 2.1.1.

For the PP population, the results of the same proportion analysis on the number of subjects with complete ulcer closure will be presented in Table 2.1.2.

The by-site summary of descriptive statistics of the number of subjects with complete ulcer closure will be presented in Table 2.1.3 for pooled sites and in Table 2.1.4 for original sites.

Individual subjects' primary efficacy data (i.e., complete ulcer closure), ulcer area measure and ulcer closure status at each visit, with and without imputation, will be listed by treatment for the ITT population (Listing 6).

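### The per-protocol rule requires completed treatment, so it drops subjects who stop for sepsis, amputation or product reaction; this part of the rule can only raise the secondary PP closure rate

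*Protocol*

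**What the plan says.** Protocol 9.3 describes the PP population as one that "is a subset of subjects in the ITT and is the secondary efficacy population". Members must be qualified and treated, and must meet a further condition: "completing the study treatment as planned in the protocol, with no major protocol deviations during the 16-week Treatment Period". Completion is therefore required in addition to the absence of major deviations. For ITT, the same section says: "The ITT population is the primary efficacy population and will be used to conduct all analyses on primary and secondary efficacy endpoints".

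Protocol 7.2 lists reasons for which subjects may be discontinued. Three concern the wound or the product: "Ulcer-related complications (i.e., life-threatening, infection-related sepsis complications"), "Subsequent limb amputation (i.e., full amputation involving the index ulcer anatomic location") and "Product-related > Grade 2 skin or systemic allergic reaction".

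SAP 2.2 separates two kinds of early stop. Subjects whose ulcer closes stop treatment and go on to the confirmatory visits. Subjects who stop before Visit 16 for any other reason are early terminations, with Visit 19 as their termination visit.

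SAP 4.5.1 repeats the primary analysis on PP: "For the PP population, the results of the same proportion analysis on the number of subjects with complete ulcer closure" goes into Table 2.1.2. SAP 3.1 does not restate the completion rule. It says: "The detailed criteria of the PP population will be provided in a separate" Data Standards document, due before database lock. SAP 3.7 gives two examples of major violations: unmet eligibility criteria without a waiver, and termination for protocol violations.

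**The concern.** A subject withdrawn for sepsis, amputation at the ulcer site or a reaction to the product has not breached the protocol. The treatment or the wound has failed, and Protocol 3 makes ulcer complications and subsequent amputation endpoints in their own right. A PP population is meant to show results when the protocol was followed. Requiring completion instead makes membership depend partly on how the wound fared: stopping through healing keeps a subject in, and stopping through one of these events takes the subject out.

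Protocol 4.2 gives response-rate estimates for powering a larger controlled trial as a purpose of the design. With one arm, no comparator shares the distortion. If the PP rate is read as the closure rate under proper treatment, some of the worst outcomes will be missing from it.

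**Working it through.** **Figures in the plan.** The visible text gives no PP size, PP closure rate or expected closure rate, so there is no planned PP figure to reproduce. The background does show how far a denominator can matter. One retrospective series is reported as 26/27 = 96.3% in Protocol 2.2 and as 26/33 = 78.8% in Protocol 2.3.2. Both reproduce, and the gap is 17.5 points. The six wounds removed there were losses to follow-up, not known failures, so this is an analogy only.

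**Inputs.**
- N = 36 enrolled, no replacement (Protocol 9.2 and 7.2).
- Dropout about 10% (Protocol 9.2): 36 × 0.10 = 3.6, about 4 subjects. No split by reason is given.
- d = subjects withdrawn without confirmed closure for sepsis complications, amputation or product reaction. Not given; taken as 0, 1 and 4.
- x = subjects healed. Not given; taken as 16 and 18, with 14 and 28 as a wider check.

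**Direction.** Protocol 3 requires closure to be confirmed at later visits, so a subject withdrawn without it is a non-healer.
- Kept and counted as not healed: x/N.
- Removed: x/(N − d).
- Difference: x·d / [N(N − d)], which is positive whenever x and d are both above zero.

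This component of the rule therefore cannot lower the rate.

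**Size.**

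| x | d | Kept | Removed | Rise (points) |
|---|---|---|---|---|
| 16 | 0 | 16/36 = 44.4% | 16/36 = 44.4% | 0 |
| 16 | 1 | 16/36 = 44.4% | 16/35 = 45.7% | 1.3 |
| 16 | 4 | 16/36 = 44.4% | 16/32 = 50.0% | 5.6 |
| 18 | 0 | 18/36 = 50.0% | 18/36 = 50.0% | 0 |
| 18 | 1 | 18/36 = 50.0% | 18/35 = 51.4% | 1.4 |
| 18 | 4 | 18/36 = 50.0% | 18/32 = 56.3% | 6.3 |

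At d = 4 the rise is 4.9 points for x = 14 (38.9% to 43.8%) and 9.7 points for x = 28 (77.8% to 87.5%). At d = 1 it is 1.1 and 2.2 points.

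**Which d is plausible.** Protocol 2.2 reports a 3% amputation rate in the retrospective series; 36 × 0.03 is about 1. Protocol 2.1 cites rates up to 51% for ulcers with limb-threatening infection. Neither figure counts the withdrawals listed in 7.2, so d stays open. d = 4 is the upper case under the planned dropout, because it leaves none for loss to follow-up or withdrawn consent.

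**The case against.** The strongest reply is that this touches only a secondary estimate whose membership is not final. ITT is primary, and Table 2.1.1 stands beside Table 2.1.2. Listing 5 names the ITT subjects left out of PP, so a reader could recompute. The detailed PP criteria sit in a document that is not available here, and the SAP's examples of major violations do not cover these events. Completing treatment is also open to interpretation: Protocol 4.4 ties study completion to Visit 19, which early terminators are asked to attend. Protocol 7.2 says subjects may be discontinued, not that they must be. The shift is also small beside the sampling error; the exact 95% interval at 18/36 runs from 32.9% to 67.1%.

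Much of this stands, and it limits the point. It does not remove it. Protocol 9.3 speaks of completing study treatment, not the study, and Protocol 8.1.3 sends those who discontinue treatment to Visit 19, so attending that visit does not show that treatment was completed. No visible text overrides 9.3, and deferring the detail leaves its rule in place. Sampling error does not excuse a one-directional shift that wording can remove.

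A reader might infer more than the documents support:
- *That the trial's main efficacy result is inflated.* It is not affected by this rule. ITT keeps these subjects, although the text on how missing outcomes are coded (SAP 2.8) is redacted.
- *That the PP rate as a whole must be too high.* Exclusions for ineligibility or other major deviations can remove healed or unhealed subjects, so the net move from ITT to PP could go either way.
- *That PP drops failures in general.* Wounds still open at Week 16 stay in as failures.
- *That the PP rate will set the Phase 3 assumptions.* Protocol 4.2 does not say which population will be used.

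**Conclusion.** The point holds for one component of the PP definition. As written, the completion condition removes non-healers who stop for sepsis complications, amputation or product reaction, and treats stopping through closure as on plan. Its effect on the secondary PP closure rate is zero or upward. With 16 to 18 of 36 healed, the rise is zero with no such withdrawals, 1.3 to 1.4 points with one, and 5.6 to 6.3 points in the upper case of four. The healed counts and d are assumptions. The result also rests on reading 9.3 plainly and on the Data Standards document not providing otherwise. This is a modest defect in a secondary analysis, worth correcting because its direction is known and the remedy is cheap.

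**What to change.** In Protocol 9.3, SAP 3.1 and the Data Standards document:
1. State that subjects who stop for ulcer-related complications, amputation, product-related reaction or death stay in PP and count as not healed.
2. Replace the completion condition, so that treated subjects leave PP only for failed eligibility or for major deviations unrelated to outcome.
3. Report the number excluded from PP, by reason, next to Table 2.1.2.

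The cost is wording in the three documents and one small table. No new data are needed, and the clinical withdrawal rules in 7.2 stay as they are. The downside is a slightly less favourable secondary PP rate. If the sponsor wants a completers-only figure, it can be shown as a labelled supplementary result beside the corrected one.
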